7.4 DATA ANALYSES

Data will be analysed using SAS 9.0 or higher. The Type I error rate for the primary study analysis will be 0.05. Comparisons for secondary, exploratory, and safety analyses will be two-sided comparisons using $\alpha = 0.05$, with no adjustment for multiple comparisons.

Primary Analysis: The primary analysis will be performed on the set of patients with non-missing CT data at 3 weeks (Full Analysis Set (FAS)). Sensitivity analyses will be presented for the intention-to-treat (ITT) patient group. A two-tailed Pearson’s Chi-Square test at $\alpha = 0.05$ will be used to assess the study hypotheses and determine whether there is a statistically significant difference between investigational and control groups with regard to the maintenance rate of immediate post-operative reduction position.

Secondary Analysis: Analyses for secondary endpoints will be on the FAS, and will only use those cases with complete data for the endpoint being analysed.

Continuous data (e.g. age, BMI) will be reported using mean, standard deviation, median, and range. Comparisons between Investigational vs Control groups with regard to continuous baseline and secondary outcomes will be performed using standard statistical tests and will be chosen as appropriate for the scale and distribution of the measures being analyzed. For example, a t-test, Wilcoxon test, or one-way ANOVA (as appropriate) may be performed to assess differences in means/medians.

Categorical data (e.g. gender, classification of fracture) will be reported using frequency and percentage. Comparisons of Investigational vs Control with regard to categorical baseline, secondary and safety outcomes will be performed using standard statistical tests and will be chosen as appropriate for the scale and distribution of the measures being analyzed. For example, categorical outcomes may be compared for investigational and control groups using the Pearson’s chi-square test.

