The Zimmer Natural Nail System Cephalomedially Asia Nail (ZNN CM Asia Nail) which was developed for Asian patients has been selling in January 2013 in Japan. While previous multi-center studies³ demonstrated the suitability of the device for the bone morphology of Japanese patients, displacement of bone fragments occurring in the early postoperative period remains a problem in treatment of trochanteric fracture with the ZNN CM Asia Nail. Fukuda et al. noted re-displacement of fracture resulting in lateral classification subtype P two weeks after surgery in 14% of patients in whom anatomical reduction was achieved immediately after surgery as confirmed by the lateral view⁴. A relatively large number of patients experiencing re-displacement are reported to have significant posterior-lateral displacement of bone fragments at the time of injury, which lead to lack of bony support posteriorly. Many researchers believe that it is desirable to have anterior-medial bony support for these patients. Maehara et al. proposed an adjunctive procedure of anterior support screw (ASS) placement which uses an additional cannulated cancellous screw anteriorly to the lag screw in order to achieve better support⁵. In ASS placement, a screw is inserted just below the anterior cortex, which is called screw augmentation technique. This prevents rotational displacement of bone fragments and may prevent the proximal reduced fragment from re-displacement. The procedure can be performed with the ZNN CM Asia Nail and standard surgical instruments without need of any special instruments.

The present study was designed to evaluate the impact of ASS's on maintenance of postoperative reduction when used in combination with the ZNN CM Asia Nail in Japanese patients who had closed trochanteric fracture.

[figure not shown]

Fig1. Screw Augmentation Technique

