2.7 ALLOWED WINDOW OF EACH SCHEDULE SEE 2.6

3. SELECTION AND WITHDRAWAL OF SUBJECTS

3.1 INCLUSION CRITERIA

In order to be eligible to participate in this study, a subject must meet all of the following criteria.

- Eligible for intramedullary nailing.
- Fracture type is classified as 3-partB or 4-part fracture in 3D-CT classification (Nakano), and combination with a subtype P in lateral classification (Ikuta) at preoperative CT assessment.
(In the case of classified in X-ray at preoperative: Classified as Type 4 or Type5 in Jensen classification, and combination of subtype P in lateral classification (Ikuta))
- Japanese Male or female
- > 20 years of age
- Primary closed intertrochanteric fracture of the femur
- Subjects willing to return for follow-up evaluations.

Study Specific Requirements for Investigator/Site

- Site can take X-ray or CT imaging, which classifies the fracture type appropriately at preoperative, also can take CT imaging at immediate postoperative and 3 weeks.

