7. STATISTICAL ANALYSIS PLAN

7.1 SAMPLE SIZE CALICULATION

The primary analysis for the study will compare the maintenance rate of immediate post-operative reduction position on the 3 week post-operative x-ray for Investigational (with ASS technique) vs. Control (without ASS technique). Sample size calculations for this study are done using data found in a paper by Maehara et al⁵. In this study, 87.5% of the patients with ASS technique were maintaining immediate post-operative reduction position, as compared to 72.7% in the conventional cohort. Our sample size calculation assumes the result in this study will be similar to what is reported in Maehara et al.

The null hypothesis is that the maintenance rate of immediate post-operative reduction position for the investigational group (with ASS technique) is less than or equal to that of the patients operated without ASS technique. The alternative hypothesis is the maintenance rate of immediate post-operative reduction position for the investigational group (with ASS technique) is greater than that of the patients operated without ASS technique.

Null Hypothesis : $H_0: \pi_A - \pi_B \leq 0$

Alternative Hypothesis : $H_A: \pi_A - \pi_B > 0$

Where π_A represents the maintenance rate of immediate post-operative reduction position in investigational group on the 3 weeks postoperative CT and π_B represents the maintenance rate of immediate post-operative reduction position in control group on the 3 weeks postoperative CT.

If we reject the null hypothesis, we can conclude that the ZMM CM Asia with ASS technique is superior to the conventional technique in trochanteric fracture with regard to the maintenance rate of immediate post-operative reduction position.

The sample size calculation was conducted anticipating the use of a Pearson's Chi-square test.

Alpha level: 5% (two sided)

Power: 80%

Investigational group maintenance rate for reduction position: 87.5%

Control group maintenance rate for reduction position: 72.7%

The resulting calculation gives $n=113$ per group. 120 patients per group will allow for up to 5% attrition.

Overall population per protocol: 240

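### The primary comparison in 7.4 leaves out a fracture class recorded before surgery; prespecified adjustment would be an optional, small efficiency gain, not the correction of an error

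*Combined protocol and SAP*

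**What the plan says.** Section 7.4 compares the arms on the primary endpoint with a two-tailed Pearson chi-square at 0.05, which "will be used to assess the study hypotheses and determine whether there is a statistically significant difference between investigational and control groups". No covariate or stratum is named. The sizing in 7.1 uses the same test: "The sample size calculation was conducted anticipating the use of a Pearson's Chi-square test".

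A fracture class is needed for entry, by one of two routes in 3.1. The CT route reads "Fracture type is classified as 3-partB or 4-part fracture in 3D-CT classification (Nakano"). The X-ray route admits Jensen type 4 or 5. Both require lateral subtype P. The schedule in 2.6 makes the preoperative classification mandatory and the preoperative CT optional. A patient classified by X-ray is reclassified on the postoperative CT.

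Section 7.2 describes blocked randomisation and mentions no stratification by fracture type. In 7.4 the classification appears only as categorical data to be tabulated and compared between arms. On prognosis, section 1.1 says: "A relatively large number of patients experiencing re-displacement are reported to have significant posterior-lateral displacement of bone fragments at the time of injury".

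**The concern.** A baseline variable that defines eligibility, is already collected and may be prognostic plays no part in the primary estimate. If it does predict loss of reduction, the unadjusted test gives up some power. Because allocation is not described as stratified by it, a chance excess of the more severe class in one arm also passes straight into the unadjusted rate difference. The planned baseline comparison might reveal such an excess, but without a prespecified adjustment any response to it would be post hoc.

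**Working it through.** **1. The plan's sample size.** Inputs from 7.1: "Alpha level: 5% (two sided"), power 80%, "Investigational group maintenance rate for reduction position: 87.5"%, "Control group maintenance rate for reduction position: 72.7"%. With pooled variance under the null and mean rate (0.875 + 0.727)/2 = 0.801:

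n = [1.960·√(2·0.801·0.199) + 0.8416·√(0.875·0.125 + 0.727·0.273)]² / 0.148²
= (1.1066 + 0.4670)² / 0.021904 = 113.05

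The plan states 113, where power is 79.98%, so the figure reproduces. The plan adds: "120 patients per group will allow for up to 5% attrition". Check: 113/0.95 = 118.9, so 119, which 120 covers. At 5% loss, 2 × 114 = 228 patients are analysed.

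**2. Fracture class alone.** Simulation with 113 per group, 40,000 trials per row and marginal rates held at 87.5% and 72.7%. The class has two levels, is known for everyone and is split 50/50. The split and the odds ratios are assumptions. Power in %:

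| Odds ratio of class | Pearson | Stratified CMH | Logistic, Wald | Logistic, LR | Change from Pearson (Wald; LR) |
|---|---|---|---|---|---|
| 1 | 80.7 | 80.4 | 80.1 | 80.8 | −0.6; +0.2 |
| 1.5 | 80.7 | 80.8 | 80.4 | 81.3 | −0.3; +0.6 |
| 2 | 80.6 | 81.1 | 80.7 | 81.6 | +0.2; +1.0 |
| 3 | 80.5 | 82.1 | 81.9 | 82.6 | +1.3; +2.1 |
| 5 | 80.8 | 83.9 | 83.7 | 84.4 | +2.8; +3.5 |

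Changes are taken from unrounded values. A 20/80 split gives nearly the same picture. The largest loss seen was with 120 per group, a 20/80 split and odds ratio 1: 83.74% against 82.91% (Wald), or −0.8 point. Type I error was 4.8% to 5.0% for all four tests.

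**3. Site and fracture class together.** Linear model for maintenance (yes/no) with arm, site and two-level class as main effects and HC2 standard errors. Assumptions: 228 patients, 15 sites (the maximum in 2.2), blocks within site, half 4-part. Two independent sets of runs (6,000 and 5,000 trials per setting), Pearson against adjusted power in %:

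| Odds ratio of class; site SD | First set | Second set |
|---|---|---|
| 1; 0 | 81.2 v 81.0 | 80.5 v 80.4 |
| 2; 0 | 80.4 v 81.1 | 80.7 v 81.4 |
| 3; 0 | 81.4 v 83.0 | 81.7 v 83.4 |
| 2; 0.5 | 81.0 v 82.7 | 81.5 v 82.9 |
| 3; 0.5 | 80.7 v 82.9 | 80.7 v 83.4 |

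With no site variation, the change is −0.2 to +1.7 points. The extra gain in the last two rows comes from the site terms, not from fracture class. A further set of runs gave −0.4 to +2.0 points over odds ratios 1 to 3. Type I error of the adjusted test lay between 4.6% and 5.7%. The upper value comes from 3,000 null trials, where the simulation standard error is √(0.05·0.95/3000) = 0.4 point.

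**4. Two classification routes.** Section 3 above the table assumes a class on one scale for everyone, which 3.1 does not guarantee. If X-ray patients form a single level and are half the sample (assumed; the share is not given), power is 81.3% against 81.1% at odds ratio 2 and 81.4% against 81.8% at odds ratio 3 (20,000 trials, no site variation). A range of −0.6 to +1.1 points covers the settings tried with this coding, and nearly all of the gain comes from site.

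**5. Chance imbalance.** With 113 per arm and a 50/50 split, the 95% range of the between-arm difference in 4-part share is ±1.96·√(2·0.25/113) = ±13.0 points. At odds ratio 3 the simulated class rates are 83.2% and 62.2% in control (gap 21.0) and 93.1% and 81.9% with ASS (gap 11.2). An imbalance at that edge moves the unadjusted difference by 0.130 × 11.2 = 1.5 to 0.130 × 21.0 = 2.7 points, against a planned difference of 14.8.

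**6. Logistic regression with site terms.** With 15 equal sites there are 228/15 = 15.2 patients per site, or 7.6 per arm. The chance that a site has no failures is (0.875·0.727)^7.6 = 0.032, and that at least one of 15 has none is 1 − 0.968^15 = 39%. Simulation gave 38% to 39%, and about 62% with site SD 0.5. Such sites have no finite site coefficient in a logistic model; the linear model has no such difficulty.

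**The case against.** The strongest case against acting is that nothing in the plan is wrong. The Pearson test controls type I error, chance imbalance included, and is the test on which the trial was sized. The planned baseline table will show any imbalance in fracture class. This stands in full, and it is why the point is optional.

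A reader might infer that adjustment raises power as a matter of course. The document does not support that. Section 1.1 ties re-displacement to posterior-lateral displacement at injury; it does not compare 3-part B with 4-part and gives no odds ratio. Entry is already limited to two fracture types, all subtype P, which may narrow the contrast.

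A reader might also infer that one common class is available preoperatively for everyone. Each patient does have a class, but in one of two systems, and X-ray patients receive the CT class only after surgery. Coding them as a single level discards their severity information and largely removes the gain from fracture class.

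Nor should it be inferred that the sponsor weighed adjustment and rejected it: the plan is silent. With fracture class alone there would be no sparse-strata reason to do so, since the two-stratum CMH test performs about as well as the main-effects model.

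What survives is that a prespecified adjustment costs little, keeps type I error near 5%, loses less than one point at worst in these runs, and protects the estimate from imbalance in the recorded class.

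**Conclusion.** An optional efficiency improvement of minor importance. Expected change in power: about 0 to 2 points if fracture class is moderately to strongly prognostic (odds ratio 2 to 3); close to zero, or a loss of up to about 0.8 point, if it is not; little or nothing from fracture class if many patients are classified by X-ray only. Adjustment also removes an imbalance effect of perhaps 1.5 to 2.7 points on the rate difference in an unlucky allocation at odds ratio 3.

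These sizes rest on the planning rates in 7.1 and on assumed values for the odds ratio, class split, X-ray share, number and size of sites, and site variation. That the primary test is unadjusted, and that a fracture class is required before surgery, rests on the text alone. Confidence is medium, because the benefit depends on a prognostic strength that the document does not report.

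**What to change.** In 7.4, prespecify a primary (or key supportive) estimate of the difference in maintenance rate with 95% CI and two-sided p-value. Take it from a linear risk-difference model with robust (for example HC2) standard errors and with arm, site and preoperative fracture class as main effects, without site-by-class strata. Report the Pearson test alongside it, and state in advance which of the two decides the trial.

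Define the class before any outcome is compared between arms, covering both routes: CT 3-part B, CT 4-part, X-ray Jensen 4, X-ray Jensen 5. Collapse the last two to a single X-ray level if few patients fall there, with the threshold fixed beforehand. Use the preoperative class, not the reclassification on postoperative CT, so that the covariate precedes treatment.

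Avoid logistic regression with site terms unless a fallback is given for sites with no failures.

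Cost: a short SAP amendment and some code, no new data, and slightly more complex reporting.

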2.3 PRIMARY AND SECONDARY ENDPOINTS

Primary Endpoint

The maintenance rate of immediate post-operative reduction position versus 3 week post-operative Re-displacement (Lateral reduction classification⁶):

- SubtypeP: Femoral head fragment fall down into diaphysis medullary space.
- SubtypeN: Even a little contact between femoral head fragment and anterior cortical bone.
- SubtypeA: Femoral head fragment located outside of medullary space..

[figure not shown]

Fig.3 Lateral reduction classification

Secondary Endpoint

- Surgery time
- Post-operative reduction position (AP3xML3)
- Pre-operative fracture classification and with or without open reduction
- CT assessment
- Safety evaluation

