3.3 SUBJECT WITHDRAWAL

It is recognized that the subject's participation in this trial is entirely voluntary, and that she/he may refuse to participate and may withdraw from participation at any time without jeopardy to any future medical care. It is also recognized that the investigator, at his/her discretion, may withdraw a subject from this study based upon his/her professional judgment. In event of subject withdrawal, applicable local procedures should be followed.

If a patient is withdrawn or rescinds their consent, a "Lost to Follow-up" case report form should be completed detailing the reason for the patient withdrawal. The site should also notify their Ethical Committee (EC) if applicable. If a patient is withdrawn from the study by the investigator, the patient should be notified of their removal by a letter from the site or according to the local EC.

It is required that patients return within the defined follow-up period to complete all study assessment forms and radiographs. Patients that miss or will not return for follow-up are not considered "protocol deviations" or "lost to follow-up."

Specific criteria for withdrawal (if applicable)

If patients meet any of the following criteria, a subject withdrawal form should be completed, and below data documented on the form:

1. Patient rescinds consent in writing: Date of occurrence
2. Patient Death: Reason and date of death should be documented
3. Implant Removal: Date of revision, all component part numbers removed, and reason for revision

Replacement of individual subjects after withdrawal

Subjects will not be replaced, unless they do not have surgery or intraoperatively it has been recognized the patient is not eligible for a treatment with ZNN CM Asia.

Follow-up of subjects withdrawn from treatment

Subject withdrawn from the study will obtain standard medical treatment as foreseen at the investigational site.

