5. ADVERSE EVENT MANAGEMENT AND REPORTING

Any adverse event should be documented on the Adverse Event case report form. A record of all adverse events, including details of the nature, onset, duration, severity, relationship to the device, relationship to the operative procedure and outcome, will be made on the relevant section(s) of the subject's CRF. The subject will be questioned about any adverse event(s) at each subsequent follow-up assessment visit.

Any serious adverse events (SAE/SADE/USADE) must be reported to head of institution and must be notified to other institutions participating in this study in accordance with Ethical Committee and Ethical Guidance for clinical study including human subject.

Adverse Event (AE):

An adverse event is any untoward medical occurrence in a patient receiving an investigational medical device that does not necessarily have to have a causal relationship with the device under investigation. An AE can therefore be any unfavorable and unintended sign (including abnormal laboratory finding), symptom, or condition temporally associated with the use of a medical device whether or not considered related to the medical device.

Serious Adverse Event (SAE):

A serious adverse event is an adverse event that

- a) led to death
 - b) led to a serious deterioration in the health of the patient that
 - c) led to fetal distress, fetal death or a congenital abnormality or birth defect
- 1) resulted in a life-threatening illness or injury

- 2) resulted in a permanent impairment of a body structure or a body function
- 3) resulted in medical or surgical intervention to prevent permanent impairment to body structure or body function
- 4) required in-patient hospitalization or prolongation of existing hospitalization

A planned hospitalization for a pre-existing condition, or a procedure required by this protocol, without serious deterioration in health, is not considered a serious adverse event.

Adverse Device Effect (ADE):

An ADE is any untoward and unintended response to an investigational medical device.

Serious Adverse Device Effect (SADE):

A SADE is any untoward and unintended response investigational medical device that has resulted in any of the consequences characteristic of a serious adverse event or that might have led to any of these consequences if suitable action had not been taken or intervention had not been made or if circumstances had been less opportune.

Unanticipated serious adverse device effect (USADE)

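### No safety analysis set is defined; as written, safety and surgery time are compared only in patients who have a 3-week CT

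*Combined protocol and SAP*

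**What the plan says.** Section 2.3 places surgery time and "Safety evaluation" in the list of secondary endpoints.

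Section 7.4 sets the population for that list: "Analyses for secondary endpoints will be on the FAS, and will only use those cases with complete data for the endpoint being analysed". It defines the FAS in the paragraph on the primary analysis: "The primary analysis will be performed on the set of patients with non-missing CT data at 3 weeks (Full Analysis Set (FAS"). The only other set named is ITT, which is used for sensitivity analyses of the primary endpoint.

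Section 7.4 mentions safety by name twice. One sentence begins "Comparisons for secondary, exploratory, and safety analyses will be two-sided comparisons" and goes on to give the alpha level and to rule out multiplicity adjustment. The other reads "Comparisons of Investigational vs Control with regard to categorical baseline, secondary and safety outcomes will be performed using standard statistical tests" and concerns the choice of test. Neither states a population.

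Section 3.3 makes death and implant removal reasons for withdrawal ("Patient Death: Reason and date of death should be documented"). Section 5 requires recording for everyone: "Any adverse event should be documented on the Adverse Event case report form". Section 9 promises a final report that covers complications and accounts for follow-up.

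**The concern.** Membership of the FAS is decided three weeks after surgery. It requires the patient to be alive, in the study and scanned. A patient who dies or leaves before then cannot be a member, and one whose implant is removed or revised early may not be scanned. These are the patients in whom early serious harm is most likely to have occurred. If one technique caused more early deaths or withdrawals than the other, the planned comparison would understate that difference or miss it, because the affected patients would be missing from both numerator and denominator.

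Patients who have an event and are still scanned remain in the comparison. The missing events are also not lost to the trial: they stay on the adverse event forms and in the final report. What is lost is their place in the between-arm comparison.

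Surgery time is a lesser matter of the same kind. It is known at operation for every operated patient, so it need not depend on a later scan.

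**Working it through.** **Which set applies.** Three statements, taken together, decide it.

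1. Safety and surgery time are secondary endpoints (section 2.3).
2. Secondary endpoints are analysed on the FAS (section 7.4).
3. The FAS requires a 3-week CT (section 7.4). Section 7.3 likewise leaves patients lost to follow-up or without that CT out of the primary analysis.

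No section defines a safety, as-treated or all-operated set.

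**How many patients this can affect.** Section 7.1 needs 113 per group and plans 120 to allow up to 5% attrition. Check: 113 / 0.95 = 118.9, so 119 would suffice and 120 is consistent. The allowance is 0.05 × 120 = 6 per arm, or 12 of 240.

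**Illustration.** All event counts below are assumptions, because the documents give none. Each patient lost before the CT is taken to have had a serious event. For a table with a, b events and non-events in one arm and c, d in the other, the Pearson statistic is N(ad − bc)² / [(a+b)(c+d)(a+c)(b+d)], without continuity correction. Fisher p-values are two-sided.

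*All events occur in patients lost before the CT:*

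| All operated | Fisher p | Pearson p | On the FAS |
|---|---|---|---|
| 6/120 vs 0/120 | 0.029 | 0.013 | 0/114 vs 0/120 |
| 5/120 vs 0/120 | 0.060 | 0.024 | 0/115 vs 0/120 |
| 6/120 vs 1/120 | 0.12 | 0.055 | 0/114 vs 0/119 |

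For the first row: 240 × (6 × 120 − 114 × 0)² / (120 × 120 × 6 × 234) = 6.15, p = 0.013.

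*Some events also occur in patients who are scanned.* Take 10/120 vs 3/120 in total, with 6 vs 0 of these patients lost before the CT.

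- All operated: 8.3% vs 2.5%, difference 5.8 points. Pearson 240 × (10 × 117 − 110 × 3)² / (120 × 120 × 13 × 227) = 3.98, p = 0.046; Fisher p = 0.084.
- FAS: 4/114 vs 3/120, that is 3.5% vs 2.5%, difference 1.0 point. Pearson 234 × (4 × 117 − 110 × 3)² / (114 × 120 × 7 × 227) = 0.21, p = 0.65; Fisher p = 0.72.

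*Equal losses.* With 6/120 vs 6/120 and 3 of the 6 lost in each arm, the FAS shows 3/117 vs 3/117. The difference stays at zero, but both rates fall from 5.0% to 2.6%. If all 6 are lost in each arm, 12 events are missing from the comparison.

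*Milder imbalance.* Counts of 3 vs 1 (Fisher p = 0.62, Pearson p = 0.31) or 4 vs 2 (Fisher p = 0.68, Pearson p = 0.41) out of 120 would not be significant even with everyone included. In these cases what the FAS loses is the description of the events, not a significant result.

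**The case against.** The strongest reply is that section 7.4 twice names safety alongside secondary, as if it were a separate class. The FAS sentence refers only to secondary endpoints, so another population may have been intended for safety. That is possible, but none is stated. If safety is a secondary endpoint, as section 2.3 says, its set is the FAS; if it is not, its set is undefined. Section 7.4 needs a sentence either way. Surgery time has no such ambiguity.

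A second reply is that section 9 counts deaths, implant removals and revisions as lost to follow-up, requires follow-up percentages and summarises complications, so these patients remain visible. This is true and limits the harm. But the accounting is not stated to be by arm, and it supplies no population for the comparison that section 7.4 plans.

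A third is that the illustrations are one-sided and the 5% allowance covers losses for any reason. Section 3.2 also excludes patients who cannot have the scans, which limits foreseeable CT loss. This stands as a caution about size: the examples show what the rule can do, not what is expected.

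Two smaller points also stand. No mechanism is apparent by which a missing CT would distort surgery time between arms, so the cost there is mainly some precision. And the plan describes no adverse event collection after withdrawal, so a wider set may have incomplete follow-up for some patients.

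**Conclusion.** The concern holds. The plan defines no safety set, and its stated rule for secondary endpoints removes patients without a 3-week CT from the between-arm comparison of safety and of surgery time. Within the planned attrition this affects up to about 6 patients per arm. Under the assumed counts, that is enough to turn a 5.0-point difference into none, or a 5.8-point difference into 1.0 point. The actual bias cannot be computed, because the documents give no event rates. It depends on how many early losses are serious events and how unevenly they fall between the arms. The primary conclusion is not affected. This should be fixed before analysis.

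**What to change.** Add a short paragraph to section 7.4, for example:

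> Safety outcomes and surgery time are analysed in all randomised patients who had study surgery, whether or not a 3-week CT exists. Deaths, implant removals and revisions are counted as events. The FAS is kept for CT-based secondary endpoints.

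The same paragraph should state:

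- whether patients are grouped by treatment received or as randomised;
- the period over which events are counted, since the 16-week visit is optional, and how patients who withdraw within that period are handled;
- that patients replaced under section 3.3 because "intraoperatively it has been recognized the patient is not eligible for a treatment with ZNN CM Asia" are reported separately.

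The cost is a few sentences. Adverse events, deaths, implant removals and surgery time are already collected, so no new data items are needed. The primary analysis and the sample size stay as they are.
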